17.4 Reporting Procedures

All AEs collected during stimulation visits will be recorded in the adverse event record of the subject's CRF. The information recorded should be based on the signs or symptoms detected during the physical examination and clinical evaluation of the subject. Signs and symptoms should be recorded using standard medical terminology.

The following AE information must be included (when applicable): the specific condition or event and direction of change; whether the condition was preexisting (i.e., an acute condition present at the start of the study or history of a chronic condition) and, if so, whether it has worsened (e.g., in severity and/or frequency); the dates and times of occurrence; duration; severity; causal relationship to the product under study ; action taken; and outcome.

IRB Reporting:

Any AE's/SAE's should also be reported in writing to the reviewing IRB, per their requirements.

MDR Reporting:

As the study device is commercially available, all adverse events also need to be reported through FDA's MDR reporting system. <https://www.accessdata.fda.gov/scripts/medwatch/>

Follow-up of Adverse Events

All AEs recorded during the study are to be followed in accordance with good medical practice until they are:

- resolved, stabilized, or judged no longer clinically significant, or
- if a chronic condition, until fully characterized, or
- for 30 days, which may extend through the follow-up phase for treatment related AEs or SAEs that occur or are ongoing at the last treatment session.

17.5 Safety Monitoring for Potential Seizure Risk

All treatment protocols in this study do not deviate from FDA cleared treatment parameters for NeuroStar TMS. All subjects will be assessed during the screening phase for neurologic disease, concurrent medication use, or other clinical factors that may contribute to the risk of seizure. Stimulation parameters maintain a safety level within the guidelines consistent with the 1998 NINDS workshop recommendations.

All personnel involved in the administration of rTMS in this study will be required to participate in individual site initiation visits and/or complete other sponsor training requirements and be able to demonstrate understanding of these issues for the sponsor prior to initiation of subject enrollment at the site.

18 STATISTICAL ANALYSIS PLAN

Statistical analyses will be performed by the Biostatistics Section of the Sponsor or its designee. Any additional or supplemental data analyses performed independently by the Investigator should be submitted to the Sponsor for review and approval.

18.1 Sample Size Considerations

A sample size of 40 total subjects, twenty to begin treatment with each of Treatments X and Y was selected as sufficient to perform a preliminary assessment of the differences between the two repetitive transcranial magnetic stimulation (rTMS) therapies for MDD. The sample size is

not based on formal power requirements for a statistical hypothesis test but is based on a desire to obtain a reasonable initial data set for exploratory and planning purposes.

18.2 Analysis Plan

The primary outcome is the difference in comfort and pain observed between rTMS stimulation protocols using VAS comfort scores. The analysis will be performed on the sample of evaluable subjects, meaning those subjects with at least one post-treatment time point.

- Descriptive analysis of subject demographics and other baseline variables.

- Primary Outcome Assessment:

The Primary study outcome will be determined based on differences in the mean VAS ratings on a 0-10cm VAS scale for comfort between treatment arms.

- Secondary Outcome Assessment:

The Secondary objectives are to evaluate the ability to reach the prescribed treatment intensity, the time it takes to reach the prescribed treatment intensity, maximum treatment intensity reached, patient treatment preference and discontinuations due to treatment discomfort. Other treatment effects between the two treatment protocols will be explored.

- Comparison of the incidence, severity, and frequency of Adverse Events (AE) between the experimental and the control group will be made descriptively.
- Statistical methods employed to detect differences between the experimental and the control groups, for the above outcomes, may include a t-test, Chi-Square test, and Fisher's Exact test. For assessments including crossovers, a relevant method accounting for period effect, repeated measures, and randomized order will be utilized.
- Subgroup analysis will be performed based on initial comfort scores, group assignments or other variables.
- More detailed descriptions of the statistical methodology and analyses will be supplied in a separate SAP (statistical analysis plan).

ADMINISTRATIVE SECTION

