10 STUDY DESIGN

10.1 General Description

This study is a prospective, randomized, single blind study to be conducted in 40 adults who have been prescribed treatment for MDD with rTMS. The study will be performed at a single site, where MDD patients, if eligible, may provide consent and participate. Prior to rTMS stimulation, the Motor Threshold (MT) will be established for each subject individually. Each subject will be evaluated for up to 2 weeks during their normal TMS treatment protocol, then exited from the study. The total study duration is expected to be approximately 6 months depending upon enrolment rate. The goal of the study is to monitor and compare patient comfort (treatment area sensitivity) using two different treatment protocols at the start of TMS

therapy where the stimulation intensity is typically escalated over 1-10 treatments until the patient is comfortable with the prescribed treatment dose (% MT; typically, 120%).

Each subject will be treated with rTMS for MDD as diagnosed and prescribed by their treating physician. All study visits will occur during the subject's normal pre-treatment evaluation and within the first 10 TMS treatment sessions. Study questionnaires will be administered during screening and during each treatment to evaluate the subject's perception of comfort specifically related to the TMS therapy provided that day.

Patients will be randomized after consent to receive either the standard Dash protocol (Treatment Y) or the modified Dash protocol with the SoftStart feature enabled (Treatment X). During all treatments, the subject will be blinded to whether they are receiving "Treatment X" or "Treatment Y".

Ramp Phase:

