Since during the first few treatment sessions patients are typically ramped up to the desired treatment intensity (%MT) in a subjective manner by the treater, this process will be standardized during the study to minimize this confounding factor on perception of comfort. For all treatments, the first session will begin at 90% MT and the treater will ask the subject if they can tolerate the treatment intensity at 5 equal time intervals per treatment session (a treatment interval is 3 minutes and 45 seconds (3:45)). If tolerance is acceptable, the treater will increase the treatment intensity by 10% with the objective of reaching 120% by the end of the first treatment session. Dosage escalations during treatment will be limited to these 5 equal time intervals; however, dosage decreases can be done at any point due to patient intolerance. Treatment intensity changes will not be communicated to the subject. The treatment intensity achieved at each interval will be logged and documented in the study CRF. After the first interval (3:45), and after each stimulation session the subject will be asked to complete a "Comfort/Pain" VAS scale from (0-10cm). Once the subject completes the last 3:45 of a treatment session at 120%MT, they will begin their Crossover phase at the start of the next session. If a subject does not reach 120% MT by the end of the fifth treatment session, dose escalation attempts will continue, but they will transition to the Crossover phase. Refer to Attachment D for details of the Dose Escalation process.

Crossover Phase:

At the start of the 6th Treatment session or the session after the subject reaches the prescribed dose, the subject will be crossed over to the alternative treatment protocol and continue to alternate treatment each day for the next 3 treatments. Each day of these 4 treatment sessions,

at the first time interval (3:45) and the end of the session the subject will complete the comfort/pain questionnaire and be asked whether they preferred the current treatment, or the treatment received at the previous session (Todays Treatment, Last Treatment, No Difference).

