If the subject reaches the prescribed %MT at any of these visits and sustains that MT through the final 3:45 minute time interval, the next study visit will be the start of the crossover phase of the study (Crossover Treatment 1). If the subject does not achieve the prescribed MT by the end of the 5th Treatment session, they will continue to Crossover Treatment 1 at the next visit, however, attempts to achieve the prescribed %MT should continue and be documented.

Crossover Phase

Visit 1

Subjects will be crossed over to the alternative treatment protocol, those who had received treatment X will then receive treatment Y and vice versa. Subjects will start treatment at the %MT established in the previous session and all study treatment assessments completed on Treatment Visits 2-5 of the Ramp Phase will be repeated and documented for each visit of the Crossover Phase.

Visits 2-4

Subjects will be crossed over to the alternative treatment protocol, those who had received treatment X will then receive treatment Y and vice versa. At the start of treatment, subjects will start treatment at the %MT established in the previous session and all study treatment assessments completed on Crossover visit 1 will be repeated.

Visit 4: Final Crossover Visit

At the start of treatment for Crossover visit 4, subjects will be crossed over to the alternative treatment protocol, subjects will start treatment at the %MT established in the previous treatment and all study treatment assessments completed on Crossover visit 1 will be repeated.

At the end of the final treatment, the treatment protocol for further TMS sessions will be determined by the clinician and the patient as part of their normal care. The treatment choice will be documented, and the subject will be exited from the study. See subject flow diagram in section 14.2 for additional information.

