15.2 Randomization

A randomization schedule will be generated by Neuronetics or a designated contract research organization (CRO). Eligible subjects will be randomly assigned to the Dash treatment protocol (Y) or Dash with the SoftStart feature enabled (X). Randomization numbers will be recorded in the screening log and on the subject's CRF. Randomization numbers may not be reassigned.

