## **4.1 Randomization**

Subjects will be randomized prior to study start, to the initial treatment received prior to first crossover. Randomization will be performed using random permuted blocks of sizes 2 and 4, stratified by gender, with a 1:1 allocation ratio (Dash protocol / Dash protocol with SoftStart). A single site handling 40 total subjects is planned. Extra subjects and sites will be randomized, in the event unforeseen changes become necessary. Randomized treatment will be assigned by paper envelopes only, no database will be utilized.

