## **6.8 Subgroup Analyses**

Subgroup analysis may also be performed based on gender, initial comfort scores, group assignments or other variables. Specifically, an examination may be done to determine if differences between treatment arms are consistent across males and females, to investigate whether females are more sensitive to pain overall, descriptively only, or additionally via one-sided hypothesis tests.

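### Subgroup tests by group assignment would split the crossover by sequence, where a steady session trend shows up as opposite-signed false SoftStart effects

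*Protocol*

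**What the plan says.** Protocol 18.2 commits to subgroup work: "Subgroup analysis will be performed based on initial comfort scores, group assignments or other variables". SAP 6.8 makes it optional and adds gender: "Subgroup analysis may also be performed based on gender, initial comfort scores, group assignments or other variables". Neither document defines the group-assignment factor further.

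SAP 4.1 says what is randomised: patients are allocated 1:1 "to the initial treatment received prior to first crossover". What follows is fixed. Protocol 10.1 says that "the subject will be crossed over to the alternative treatment protocol and continue to alternate treatment each day for the next 3 treatments", and Protocol 13.1 repeats for each crossover visit that "those who had received treatment X will then receive treatment Y and vice versa".

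The plan recognises period effects. For crossover assessments, Protocol 18.2 promises a method that handles period, repeated measures and order. SAP 6.6.2 turns that promise into an option. Neither text says how session effects would be handled inside a single-sequence subgroup, or how a difference between the two subgroups should be read.

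**The concern.** Because alternation is deterministic, group assignment and sequence are the same thing. Within one sequence each protocol always occupies the same crossover sessions, so anything that changes comfort from session to session is mixed with the protocol difference. The mixing has one sign in SoftStart-first patients and the other sign in Dash-first patients.

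The documents give reason to expect such change. Protocol 10.1 describes practice in which "the stimulation intensity is typically escalated over 1-10 treatments until the patient is comfortable with the prescribed treatment dose". For patients not at target after five sessions it adds that "dose escalation attempts will continue, but they will transition to the Crossover phase", so intensity can still rise during the crossover phase.

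At stake is a statement that SoftStart helps patients who start on one protocol but not those who start on the other, when the data show only a session trend. The study is meant for exploration and planning (Protocol 18.1), and such a statement could misdirect that planning.

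**Working it through.** The plan gives no effect size, SD or power (Protocol 18.1, SAP 5), so there is no figure to reproduce. The check is design algebra followed by an illustration under stated assumptions.

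**Inputs from the documents**
- Two sequences with 20 patients planned in each (Protocol 18.1).
- Four crossover sessions (schedules of events in both documents).
- SoftStart-first patients run Y,X,Y,X and Dash-first patients run X,Y,X,Y (Protocol 13.1).
- Most tests are one-sided for superiority of X (SAP 6.6.2.1).
- VAS scored 0 to 100 on a 10 cm line, higher being worse (SAP 6.6.2), so units below are mm.

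**Step 1: bias within one sequence.** Let p1 to p4 be session effects common to both sequences, with a true treatment effect of zero.
- SoftStart-first: mean X minus mean Y = (p2+p4)/2 - (p1+p3)/2 = d.
- Dash-first: mean X minus mean Y = (p1+p3)/2 - (p2+p4)/2 = -d.
- Equal-weight average of the two: (d - d)/2 = 0.

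For a strictly monotone trend, p2-p1 and p4-p3 have the same sign, so d is not zero. For a linear trend of b per session, d = [(2b+4b) - (b+3b)]/2 = b, and the subgroups differ by 2b. If p1+p3 = p2+p4, for example a single step exactly between sessions 2 and 3, then d = 0.

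**Step 2: can a period-adjusted model rescue the split?** Let E = 1 in even sessions, S = 1 for Dash-first and T = 1 under SoftStart. Then T = E + S - 2ES, and the interaction T×S = S - ES = (S + T - E)/2. The interaction is an exact combination of terms already in the model. In rank terms:
- free sessions + sequence + treatment: 6 of 6 columns, estimable;
- the same plus treatment-by-sequence: 6 of 7, not estimable;
- one sequence alone, free sessions + treatment: 4 of 5, not estimable.

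If the trend is assumed linear, one sequence is enough. For Y,X,Y,X the contrast (-y1 + 3y2 - 3y3 + y4)/4 has treatment weight (3+1)/4 = 1 and trend weight (-1+6-9+4)/4 = 0. With independent errors of equal variance across sessions, its variance factor is (1+9+9+1)/16 = 1.25, against 4 × (1/2)² = 1 for the simple difference.

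**Step 3: size.** Assumptions:
- no true effect, and complete data on 20 patients per sequence;
- unadjusted t-tests: one-sided 5% within each subgroup (the level is assumed, because the SAP gives 0.05 only as two-sided) and two-sided 5% between subgroups;
- scores falling by b per session;
- SD s of the within-patient X minus Y difference.

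Within a subgroup the noncentrality is ±b√20/s on 19 df. Between subgroups it is 2b/(s√(2/20)) on 38 df. For example, b = 2 and s = 15 give 0.596 and 0.843.

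| s (mm) | b (mm/session) | SoftStart-first positive | Dash-first positive | Subgroups differ |
|---|---|---|---|---|
| 10 | 2 | 21.7% | 0.61% | 23.4% |
| 10 | 4 | 53.2% | 0.04% | 69.3% |
| 15 | 2 | 14.2% | 1.3% | 13.0% |
| 15 | 4 | 31.0% | 0.26% | 37.6% |
| 20 | 2 | 11.3% | 1.9% | 9.5% |
| 20 | 4 | 21.7% | 0.61% | 23.4% |

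Each rate would be 5% without a trend.

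**Step 4: whole-trial average.** SAP 6.6.2 also lists an average over ramp and crossover phases. There the bias depends on ramp length. With a two-session ramp, SoftStart-first patients have X at sessions 1, 2, 4, 6 (mean 3.25) and Y at 3, 5 (mean 4), so a linear trend contributes -0.75b. With a five-session ramp it contributes 31/7 - 7 = -2.57b. With a one-session ramp it contributes 0. Dash-first patients have the opposite sign.

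**The case against.** The strongest reply is that Protocol 18.2 already promises a method accounting for period and order, in the sentence group just before the subgroup list, so unadjusted subgroup tests are not what the plan must produce. This stands in part: the rates above describe an unadjusted split and are not a forecast of the trial's analysis. The promise nevertheless protects only the pooled comparison. With free session effects no sequence-specific treatment effect can be estimated, and neither document names a trend shape that would identify one.

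A reader might infer that every session trend distorts the split, or that only averaging over the sequences removes it. Neither follows. Trends with p1+p3 = p2+p4 leave no bias, and a linear trend can be removed within a sequence at 1.25 times the variance.

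A reader might also infer that the primary comparison is compromised. It is not, on this account, when the two sequences carry equal weight.

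The scope is also open to challenge. The factor is undefined, and a breakdown by assignment of time to target intensity or of ramp-phase comfort would not have this problem. That stands, and the point is confined to X minus Y comparisons that use crossover sessions. Results by sequence are a useful check on order effects, which is a reason to keep them as a display.

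Finally, SAP 4 speaks of alternating for the next 4 treatments where Protocol 10.1 has 3. Read as five crossover sessions, a linear trend would cancel within each sequence. The working uses four because both schedules, and SAP 4's own next paragraph, show four; the texts need reconciling.

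**Conclusion.** The point holds for subgroup tests of the crossover-phase X minus Y comfort difference by group assignment. Any strictly monotone session trend then gives equal and opposite false effects in the two subgroups, and the promised period adjustment cannot separate them without an assumed trend shape.

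Over the assumed range (SD 10 to 20 mm, habituation 2 to 4 mm per session), false-positive rates are 11% to 53% in SoftStart-first and 0.04% to 1.9% in Dash-first patients, and a spurious subgroup difference appears in 9% to 69% of trials. These figures rest on assumed SDs and trends, session effects common to both sequences, 20 complete patients in each, and unadjusted tests.

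The weight is minor. The study is exploratory, the SAP makes the subgroup work optional, and the equally weighted pooled comparison is untouched.

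**What to change.** In SAP 6.8, remove group assignment as a factor for subgroup tests of the treatment effect, and make the matching change in Protocol 18.2 at the next amendment. Add one sentence to the SAP: the crossover treatment effect is taken from a joint model with session, sequence and treatment; X minus Y results by sequence may be shown descriptively as a check on session and order effects, but are not tested or interpreted as subgroup effects.

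The cost is a short text edit with no change to data collection. The protocol edit is best held for the next amendment because, if judged significant, it would need IRB approval under Protocol 19.7. The one loss is that there would be no inferential result by sequence.

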19 INVESTIGATOR OBLIGATIONS

19.1 Institutional Review Board (IRB) Approval

No subjects will be enrolled at the investigational site until full approval is obtained from the institutions IRB for both the protocol and the informed consent document.

The protocol and the informed consent document must have the initial and at least annual (when required) approval of an IRB. The signed IRB approval letter must identify the documents approved (i.e., list the Investigator's name, the protocol number and title, the date of the protocol and informed consent document, and the date of approval of the protocol and the informed consent document).

19.2 Pre-study Documentation

The Investigator must provide the Sponsor with the following documents prior to enrolling any subjects:

- Protocol Investigator Agreement/Investigator Signature (see p. 6 of protocol)
- Current signed and dated curricula vitae for the Investigator, sub-Investigators, and all key personnel listed on the clinical study information form.
- Copy of the IRB approval letter for the protocol and informed consent. Written assurance of continuing approval (at least annually) as well as a copy of the annual progress report submitted to the IRB must also be provided to the sponsor. Any changes in this study or unanticipated problems involving risks to the subjects must be reported promptly to the IRB. An Investigator must not make any changes in a study without IRB and sponsor approval except when necessary to eliminate apparent immediate hazards to the subjects. All protocol amendments must be submitted to the IRB and approved.
- Copy of the IRB-approved informed consent document to be used.
- When applicable, a list of the IRB members and their qualifications, and a description of the committee's working procedure.
- Financial disclosure statement.
- Fully executed clinical study agreement (CSA).

19.3 Informed Consent and HIPAA Authorization

Subject's written informed consent will be obtained prior to enrolment in the study, disclosing all known and potential risks, including societal, of rTMS. A copy of the consent form will be given to each subject.

Subject confidentiality will be protected throughout the course of the study.

The informed consent document shall contain all of the elements of informed consent specified in the regulations. Some regulations may require the disclosure of additional information to the subject and/or inclusion of additional information in an informed consent document. Copies of the regulations relating to informed consent and the protection of human subjects in clinical studies are available from the Sponsor.

Nothing in these regulations is intended to limit the authority of a physician to provide emergency medical care under applicable regulations. In addition, some regulations require the permission of regulatory agencies to conduct inspections and review records pertaining to this clinical investigation.

The delegation of Investigator responsibilities including informed consent will be documented on the clinical study information form. Health Insurance Portability and Accountability Act (HIPAA) authorization must be signed by all study subjects prior to any procedures for the study being conducted.

